### **10.2. SECONDARY ANALYSIS**

Secondary analysis of the retrospective data set will be both descriptive and statistical, as follows.

#### **10.2.1. Subject Demographics**

Descriptive evaluation (mean, standard deviation and range) of the subject demographics of age and gender will be performed on a subject rather than lesion basis.

#### **10.2.2. Lesion Variables**

- (i) *Lesion Type and Location*: The distribution (number and percentage) of lesion type (BCC and SCC) and the distribution of lesion subtype within each lesion type will be

calculated. The distribution of the location of lesions on the body will also be calculated. The findings will be presented descriptively in table and chart format.

- (ii) *Comorbidities*: The distribution (number and percentage) of comorbidities for lesions overall and by lesion type will be calculated and presented descriptively in table and chart format.
- (iii) *Lesion Size*: Descriptive evaluation (mean, standard deviation and range) of baseline lesion size (diameter) in centimeters (cm) will be calculated for lesions overall and by lesion type. T-test analysis for two independent samples will be applied to assess for any difference in lesion size between lesion types. A two-tailed p value of <0.05 will be considered statistically significant and indicative of a clinically meaningful difference. The categorical distribution (number and percentage) of lesion size for all lesions and by lesion type will also be calculated.

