#### **1.5. CAUSE OF NON-MELANOMA SKIN CANCER (NMSC)**

NMSC primarily results from repeated and unprotected skin exposure to ultraviolet (UV) rays from sunlight and man-made sources such as tanning beds. UV rays can damage the DNA inside skin cells that comprise genes that control cell function.

It is believed that most NMSC are the result of DNA changes from UV ray exposure that affect the tumor suppressor genes in cells. Tumor suppressor genes are those that keep cell growth in check by slowing down cell division or causing cells to die at the right time. The gene most often altered in SCC is TP53, the tumor suppressor gene that normally functions to cause cells with damaged DNA to die. When TP53 is altered, these abnormal cells may live longer and proceed to become cancerous.

In BCC, the most common mutated gene is PTCH1, a tumor suppressor gene that typically functions to keep cell growth in check. Changes to PTCH1 permit cells to grow out of control.

These are not the only gene changes that play a role in the development of skin cancer. There are likely to be many others as well.

Additional risk factors for the development of NMSC include radiation therapy, lighter skin, prolonged immunosuppression, human immunodeficiency virus (HIV), human papilloma virus (HPV), and certain syndromes or genetic disorders.

Increased risk of multiple NMSC lesions is associated with males, tumor locations in the trunk and extremities, superficial histologic subtype, younger age at initial diagnosis, and red hair phenotype.

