### **5.4.1. Inclusion Criteria**

1. Male or female.
2. Treatment with SRT-100™.
3. Treatment date of December 31, 2015 or earlier.
4. Non-Melanoma Skin Cancer (NMSC) pathological diagnosis of confirmed squamous cell carcinoma (SCC) or basal cell carcinoma (BCC).

5. Histopathological Grade: G1 (well differentiated); G2 (moderately differentiated) or Gx (not assessed).
6. One lesion is treated, or more than one lesion is treated with a minimum of a 5 mm gap between the edges of the lesion margins.
7. Required retrospective data is existing and sufficient.

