#### **A. Patient Information and Demographics:**

1. Gender
2. Age at treatment start

3. Ethnicity
4. Significant comorbidities

B. Lesion Diagnostic Variables and Characteristics:

1. Pathology diagnosis
2. Diagnosis subtype/variant
3. Other pathology
4. Recurrent lesion (yes/no)
5. Previous treatment if recurrent
6. Lesion location (no restrictions): scalp, mastoid, forehead, cheek, nose, ear, chin, lips, neck, upper arm, lower arm, hand, upper leg, lower leg, foot.

C. Lesion Size and Margins:

1. Lesion size
2. Treatment margin
3. Lead cutout size
4. Applicator size

D. Treatment Dosage and Schedule:

1. Treatment dose
2. Number of treatments
3. Number of treatments per week
4. Treatment span(days)

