#### **10.1.1. Cure Rate**

Cure rate will be calculated as the percentage of lesions that attained complete cure following treatment completion, reported as the overall success rate.

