#### **10.1.2. Recurrences and Complications**

Each identified incidence of lesion recurrence, complication or adverse event recorded at any point throughout the treatment and follow-up evaluation phase will be explored descriptively. Statistical evaluation of recurrences will be as follows:

- (i) *Kaplan-Meier Survival Probability Estimates* will be calculated across the duration of available follow-up data, reporting survival probability estimates, and lower and upper limits of the 95% Confidence Interval by follow-up year.
- (ii) *Log-Rank Test* will be performed to evaluate for differences in recurrence-free survival between lesion types.
- (iii) *Multivariate Cox Regression Analysis* will be performed to account for the contribution of the potential influential factors of gender, age, lesion type, lesion size, total treatment dosage and TDF to recurrence-free survival.

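### Comorbidities are recorded per patient but tabulated only per lesion, so patients with several lesions are counted repeatedly and the percentages are lesion-weighted

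*Combined protocol and SAP*

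**What the plan says.** Section 6.3 lists "Significant comorbidities" as the fourth item under patient information and demographics, alongside gender, age and ethnicity. It is recorded as an attribute of the person.

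Section 10.2.1 sets the unit of analysis for two of these attributes: descriptive evaluation of the "demographics of age and gender will be performed on a subject rather than lesion basis". Comorbidities are not mentioned there. They appear in section 10.2.2, among the lesion variables, where item (ii) states: "The distribution (number and percentage) of comorbidities for lesions overall and by lesion type will be calculated". Section 10 contains no per-subject comorbidity table.

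The inclusion criteria in section 5.4.1 admit patients with several lesions: "One lesion is treated, or more than one lesion is treated with a minimum of a 5 mm gap" between lesion margins. No maximum number of lesions per patient is given. The cure rate in section 10.1.1 is also lesion-based, as the "percentage of lesions that attained complete cure following treatment completion".

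**The concern.** The plan summarises age and gender by subject but moves a third patient attribute to the lesion level without giving a reason. A patient with six treated lesions and one comorbidity adds six to the comorbidity count. A patient with both a BCC and an SCC also appears under both lesion types, so the two columns do not describe separate groups of people.

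The comorbidity profile carries some weight in this study. Section 1.8 presents SRT as an option for patients who decline surgery or are poor candidates for it, and says that comorbidities complicate treatment choice in the elderly. Section 3 says that the findings will generalise to the wider patient population. A reader judging that claim needs to know what share of the treated patients had each condition, and the planned table does not give it.

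**Working it through.** The documents state no comorbidity prevalence, sample size or expected number of lesions per study patient, so there is no planned figure to reproduce. What follows illustrates how the planned table behaves.

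**Inputs**
- p, the proportion of patients with a given comorbidity: assumed, 5%, 10% or 20%.
- r, the mean lesions per affected patient divided by the mean per unaffected patient: assumed, 0.75 to 3.
- Mean lesions per person, for counts only: 5.4 million / 3.3 million = 1.64, from the national annual figures in section 1.4. This is background and not an estimate for patients treated with the SRT-100.

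**Step 1: percentages.** The share of lesions belonging to affected patients is

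p·r / (p·r + 1 − p).

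For p = 0.10 and r = 2 this is 0.20 / (0.20 + 0.90) = 18.2%. For r = 0.75 it is 0.075 / (0.075 + 0.90) = 7.7%.

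| Patient prevalence | r = 0.75 | r = 1 | r = 1.5 | r = 2 | r = 3 |
|---|---|---|---|---|---|
| 5% | 3.8% | 5.0% | 7.3% | 9.5% | 13.6% |
| 10% | 7.7% | 10.0% | 14.3% | 18.2% | 25.0% |
| 20% | 15.8% | 20.0% | 27.3% | 33.3% | 42.9% |

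The percentage equals the patient prevalence only at r = 1. Above that it is too high as a statement about patients, and below it too low.

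**Step 2: counts.** Take 1,000 patients, 100 of them affected, with the overall mean held at 1.636 lesions (1,636 lesions in all). Unaffected patients average 1.636 / (p·r + 1 − p) lesions, and affected patients r times that.
- r = 0.75: 1.636 / 0.975 = 1.678, times 0.75 = 1.259, so about 126 lesion rows.
- r = 1: 1.636 each, so about 164 lesion rows.
- r = 2: 1.636 / 1.10 = 1.488, times 2 = 2.975, so about 298 lesion rows.

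The count exceeds the 100 affected patients in all three cases, including the one where the percentage falls. Repetition in the count follows from the plan's wording as soon as any affected patient has more than one lesion. A shift in the percentage needs the further condition that r differs from 1.

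**Step 3: per-subject table.** If each patient is counted once, the count is 100 and the percentage is 10% whatever r is.

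**The case against.** **A per-lesion table is legitimate.** The table is described as being for lesions, stands under lesion variables, and matches the denominator of the cure rate. It correctly describes the lesion sample. This stands: the gap is the missing per-subject table, and the lesion table need not be withdrawn.

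**A reader might infer that prevalence will certainly be overstated.** Section 1.5 names "prolonged immunosuppression, human immunodeficiency virus (HIV), human papilloma virus (HPV), and certain syndromes or genetic disorders" among the risk factors for developing NMSC, which makes more lesions in such patients plausible. But the same section has a separate list of factors for multiple lesions (male sex, trunk and extremity sites, superficial subtype, younger age at first diagnosis, red hair), and it contains no comorbidity. Item A.4 also covers all significant comorbidities, not only immune ones. Section 1.8 mentions comorbidities in connection with the elderly, while section 1.5 ties multiple lesions to younger age at first diagnosis. For common age-related conditions any hint points the other way. The direction is not established.

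**A reader might also infer that the Cox model is deficient because immunosuppression is unadjusted.** Section 10.1.2(iii) lists the "potential influential factors of gender, age, lesion type, lesion size, total treatment dosage and TDF" and no comorbidity. However, the documents link immunosuppression to developing NMSC and nowhere to recurrence after SRT. The secondary objective in section 5.1.2 gives demographics as its example of patient characteristics, and age and gender are in the model. With no comparator arm, omitting the covariate does not bias the overall cure rate or the overall Kaplan-Meier estimates. The approximate effect on the lesion-type hazard ratio is [p₁(HR − 1) + 1] / [p₀(HR − 1) + 1], where p₁ and p₀ are the prevalences in the two lesion types and HR is the factor's hazard ratio for recurrence. It is 1.00 if prevalence is balanced. For an assumed 10% against 5%, it is 1.05 / 1.025 = 1.02 at HR 1.5 and 1.20 / 1.10 = 1.09 at HR 3. All of these inputs are assumptions.

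**Conclusion.** The mismatch of units is plain from the text: a patient-level item is reported only by lesion, in a study that admits any number of lesions per patient. The counts will overstate the number of affected patients whenever any of them has more than one lesion. The percentages do not estimate patient prevalence unless affected and unaffected patients have the same mean number of lesions. At an assumed 10% prevalence the table would show anything from 7.7% to 25.0% as the lesion ratio goes from 0.75 to 3, with no error at a ratio of 1. Both the prevalence and the ratios are assumptions, and the documents favour neither direction.

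The consequence is limited to the description of the treated population. Cure rate, Kaplan-Meier estimates, log-rank test and Cox model are unaffected. The absence of immunosuppression from the Cox model is a choice of covariates that the documents do not show to be wrong.

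**What to change.** Change section 10.2.2(ii) so that comorbidities are tabulated once per subject, with number and percentage, overall and by subject group: BCC only, SCC only, and both. The third group keeps patients with both tumour types from being counted twice. A per-lesion table may be kept beside it if it is labelled as lesion-weighted.

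The de-identified patient codes described in sections 7 and 7.2.1 should be enough to collapse lesion rows to subjects, provided that each lesion row carries its patient's code. No new abstraction is needed, and the planned destruction of the code-to-chart link does not stand in the way. The cost is a change of SAP wording and one extra table.

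A Cox model with an immunosuppression term is at most an optional sensitivity analysis. Immunosuppression is not a separate data field, so item A.4 may not distinguish absent from not documented. Coding it could require a return to the charts before the link is destroyed. A patient-level covariate in a lesion-level model would also need variances clustered by patient.

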### Objectives

- The primary objective of this retrospective analysis is to evaluate long-term efficacy and safety of SRT when applied with the Sensus Healthcare SRT-100™ in the treatment of NMSC.
- The secondary objectives of this study are to evaluate the data for potential differences in cure rates with respect to lesion variables (tumor size, location and type) and patient demographics; and to evaluate the relationship between outcomes and treatment dosage/fractionation.

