While formal long-term outcome evaluations may be lacking, there is much existing data. This study will utilize retrospective chart analysis to evaluate the outcomes of SRT-100™ therapy on NMSC lesions over a long-term post-treatment period. Long-term cure rate is considered the primary outcome, with secondary outcome evaluation focused on the impact on cure rate and other treatment outcomes of key variables such as lesion type, location, patient characteristics and treatment parameters such as treatment dosing and fractionation.

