#### **5.1.2. Secondary Objectives**

The secondary objectives of this study are to evaluate the retrospective data for potential differences in treatment outcomes, including cure rates, based on lesion variables (such as tumor size and location, tumor type), patient characteristics (such as demographics), and treatment dosage/fractionation differences.

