### **5.3.2. Total Number of Study Sites/Total Number of Subjects Projected**

There will be multiple participating study sites, all located in the United States. Each will be selected based upon having access to the required medical records of patients who were treated at their site for NMSC with the SRT-100™ prior to January 1, 2015, and for whom follow-up data is available. There is no limit on the potential number of participating sites. Each identified and qualifying site that is willing and able to participate in the study will be included.

Subject data will be retrospectively collected from the existing medical records in the identified qualifying patient files at the participating sites as those who were treated with the SRT-100™ for one or more NMSCs, who have follow-up data and who subsequently satisfy all of the inclusion criteria and none of the exclusion criteria for inclusion of their retrospective data in this study. There is no limit on the potential number of study subjects. The applicable retrospective data for each identified and qualifying subject at each participating study site will be included in the retrospective analysis.

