### **10.2.3. Treatment and Follow-Up**

- (i) *Treatment Period*: Descriptive evaluation (mean, standard deviation and range) of the number of treatment days will be calculated for lesions overall and by lesion type. T-test analysis for two independent samples will be applied to assess for any difference in the number of treatment days (the treatment administration period) between lesion types. A two-tailed p value of <0.05 will be considered statistically significant and indicative of a clinically meaningful difference.
- (ii) *Follow-Up Evaluation Period*: Descriptive evaluation (mean, standard deviation and range) of the number of follow-up months will be calculated for lesions overall and by lesion type. T-test analysis for two independent samples will be applied to assess for any difference in the number of follow-up months (the follow-up evaluation period) between lesion types. A two-tailed p value of <0.05 will be considered statistically significant and indicative of a clinically meaningful difference. The categorical distribution (number and percentage) of the follow-up evaluation period by year for all lesions and by lesion type will also be calculated.

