**10.2.4. Treatment Dosage and Schedule**

- (i) *Treatment Dosage*: Descriptive evaluation (mean, standard deviation and range) of the treatment dosage variables of total dosage, Fx Dose, TDF and KV will be calculated for lesions overall and by lesion type. T-test analysis for two independent samples will be applied to assess for any differences in each of the dosage variables between lesion types. A two-tailed p value of  $<0.05$  will be considered statistically significant and indicative of a clinically meaningful difference.
- (ii) *Treatment Frequency*: Descriptive evaluation (mean, standard deviation and range) of treatment frequency (number of treatment visits and number of treatment visits per week) will be calculated for lesions overall and by lesion type. T-test analysis for two independent samples will be applied to assess for any difference in treatment frequency between lesion types. A two-tailed p value of  $<0.05$  will be considered statistically significant and indicative of a clinically meaningful difference.

Furthermore, the categorical distribution (number and percentage) of the number of treatment visits and of the frequency of treatment visits per week will be calculated for lesions overall and by lesion type.

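### Section 10.2 treats p<0.05 as proof of a clinically meaningful difference in nine BCC-SCC comparisons; separately, lesion location, named in the secondary objective, has no planned outcome estimate

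*Combined protocol and SAP*

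**What the plan says.** **The rule for the t-tests.** For lesion size, section 10.2.2 (iii) states: "A two-tailed p value of <0.05 will be considered statistically significant and indicative of a clinically meaningful difference". Sections 10.2.3 (i) and (ii) and 10.2.4 (i) and (ii) repeat it, each saying that such a p value "will be considered statistically significant and indicative of a clinically meaningful difference". In 10.2.4 (i) the t-test "will be applied to assess for any differences in each of the dosage variables between lesion types", so one sentence there covers four tests. The plan gives no minimum important difference for any variable. On size, section 5.3.2 says: "There is no limit on the potential number of study subjects". Section 5.4.1 admits patients in whom "more than one lesion is treated with a minimum of a 5 mm gap between the edges of the lesion margins", while the t-test is specified for two independent samples.

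**The objective and its analyses.** The Abstract's secondary objective is to "evaluate the data for potential differences in cure rates with respect to lesion variables (tumor size, location and type) and patient demographics", together with the relation of outcome to dosage and fractionation. Section 5.1.2 asks about "potential differences in treatment outcomes, including cure rates, based on lesion variables (such as tumor size and location, tumor type", then adds patient characteristics and dosage/fractionation. Section 2 says "Long-term cure rate is considered the primary outcome" and gives location among its example factors. Location and ethnicity are collected (section 6.3, A and B). Section 10.1.1 reports cure as one overall percentage of lesions. Section 10.1.2 plans Kaplan-Meier estimates, a log-rank test by lesion type, and a Cox model with gender, age, lesion type, lesion size, total dosage and TDF. Section 10.2.2 (i) tabulates the distribution of location.

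**The concern.** A p value does not measure how large or important a difference is. With no stated minimum important difference, the smallest difference that earns the label depends, in SD units, only on how many lesions the sites find. A report that follows the plan would call a small or chance BCC-SCC difference in a descriptor clinically meaningful. Because the rule also covers follow-up months, it would attach clinical meaning to a difference in how long the two lesion types were observed.

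The second part is a gap between objective and analysis. A reader of the secondary objective expects some outcome by location. Section 10 provides none, for either cure or recurrence, although the data are collected.

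**Working it through.** The plan states no sample size, power or event count, so it has no figure of its own to reproduce. The figures in steps 2 and 3 are illustrations.

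**1. Count of statements and tests.** Statements: 10.2.2 has 1, 10.2.3 has 2, 10.2.4 has 2; total 5. Tests governed:
- lesion size (1)
- treatment days and follow-up months (2)
- total dosage, Fx Dose, TDF and KV (4)
- treatment visits and visits per week (2)

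Total 1 + 2 + 4 + 2 = 9. None tests cure or recurrence.

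**2. Smallest observed difference that earns the label.** Normal approximation, lesions treated as independent, in SD units: 1.96 × √(1/n₁ + 1/n₂).

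| BCC / SCC lesions | Source | Smallest difference |
|---|---|---|
| 100 / 140 | assumed | 1.96 × √(1/100 + 1/140) = 0.257 SD |
| 250 / 350 | assumed | 1.96 × √(1/250 + 1/350) = 0.162 SD |
| 712 / 994 | series cited in section 3 | 1.96 × √(1/712 + 1/994) = 0.096 SD |

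**3. Chance of at least one label when all nine true differences are zero.** If the tests were independent, each at its nominal 5% level: 1 − 0.95⁹ = 0.370. They are not independent, because the dosage, visit and treatment-duration variables are linked. The within-patient clustering that the t-test ignores may also move each test away from 5%. The 37% is therefore a reference value and not a forecast.

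**4. Objective set against planned outcome analysis.**

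| Factor | Recurrence (10.1.2) | Cure Yes/No item (10.1.1) |
|---|---|---|
| Lesion type | log-rank and Cox | overall percentage only |
| Lesion size, age, gender | Cox | overall percentage only |
| Total dosage, TDF | Cox | overall percentage only |
| Location | none | overall percentage only |
| Ethnicity | none | overall percentage only |
| Fractionation other than through TDF | none | overall percentage only |

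The right-hand column matters only on one reading of cure. Section 6.3 records cured Yes/No (E) separately from recurrence Yes/No (F), and 10.1.1 refers to cure after treatment completion. On that reading, cure by any factor is unplanned. If long-term cure in section 2 means freedom from recurrence, the middle column applies and the Cox model already serves six factors. Location, ethnicity and fractionation other than through TDF are unserved on either reading.

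**5. Whether location belongs in the Cox model.** The intervals quoted in section 3 give a rough guide to information in a series of that kind.
- 2 years: SE = (0.027 − 0.010)/3.92 = 0.00434; effective n = 0.019 × 0.981/SE² = 991; effective events about 19.
- 5 years: SE = (0.067 − 0.032)/3.92 = 0.00893; effective n = 0.05 × 0.95/SE² = 596; effective events about 30.

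With one term per factor, the six existing terms would have 19/6 = 3.2 to 30/6 = 5.0 events each. Location as two more terms would give 19/8 = 2.4 to 30/8 = 3.8. The actual event count of that series is not given, and this registry's size is open, so this is only a reason for not enlarging the model by default.

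**The case against.** **On the t-tests.** The strongest reply is that this is a matter of wording. No outcome test and no decision in the plan depends on the label. Sections 10.2.2 to 10.2.4 already require means, SDs and ranges by lesion type, so a reader sees the size of each difference beside its p value. The lesion counts used above are assumed or belong to another, single-site series. All of that stands and limits the weight of the point. It does not rescue the sentence, which prescribes a wrong interpretation in five places.

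**On location.** Section 2 and section 5.1.2 offer location as an example; only the Abstract lists it outright. Section 10.1.2 also says that each recurrence will be described, which could include its site. The first point stands and makes this an improvement rather than an error. The second does not fill the gap: describing individual recurrences is not a rate by location with a denominator.

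**Stronger readings that the documents do not support.** A reader might infer that the primary results are compromised; the overall cure percentage and Kaplan-Meier estimates use neither the label nor location. A reader might infer that no secondary factor has an outcome analysis; the Cox model covers six. A reader might infer the opposite, that location is the only factor left out; ethnicity, and fractionation other than through TDF, are left out too.

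**Conclusion.** **Part 1 is wrong as written and should be corrected.** Five sentences, governing nine descriptor comparisons, equate two-tailed p<0.05 with clinical meaning. This follows from the text and needs no assumption. The illustrations (0.26 SD at 100/140 lesions, 0.096 SD at 712/994, and 37% for nine true nulls) rest on assumed or borrowed lesion counts, independent lesions and, for the last, independent tests. The effect is confined to how the BCC-SCC descriptor comparisons are interpreted.

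**Part 2 is a cheap improvement.** Location is named in the objective and collected, but section 10 has no cure or recurrence estimate by location on either reading of cure. Whether cure by the other factors is also unplanned depends on what cure means, which the plan leaves open.

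**What to change.** **Sections 10.2.2 to 10.2.4.** In all five places, delete the clause that turns statistical significance into clinical meaning. Report each BCC-SCC mean difference with a 95% CI that allows for several lesions per patient. For KV, which section 6.3 records as one of three settings, report the distribution by lesion type instead. Label the comparisons descriptive. This changes no outcome estimate; the only work is the clustered intervals.

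**Section 10.1.1.** State whether long-term cure means the Yes/No item or freedom from recurrence. Add a descriptive table of cure (Yes/No) with patient-clustered 95% CIs by the factors named in the objective, including location and number of fractions. Label it exploratory, without tests.

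**Section 10.1.2.** Add Kaplan-Meier recurrence-free estimates with patient-clustered 95% CIs by location, grouped into a few categories fixed before analysis. Label them exploratory, without tests. Keep them whatever the event count, and leave the Cox list unchanged. If the sponsor does not want these estimates, remove location from the objective instead.

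**Cost.** The additions use data already collected and yield a few imprecise, unadjusted subgroup estimates. At an assumed cure rate of 98%, the Wilson 95% CI is 93.0% to 99.4% for 98 of 100 lesions and 89.5% to 99.6% for 49 of 50, before allowing for clustering.
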